Patients will be recruited from sports medicine, family medicine, orthopedic, geriatric, and rheumatology clinics. Participating clinicians and research partners will identify patients with moderate or severe pain secondary to primary osteoarthritis (using the Kellgren-Lawrence Scale) who have persistent knee pain refractory to all attempted medical therapies and lifestyle modifications. The clinician will notify one of the GAE research team members. The patient will then be scheduled for consultation in the Interventional Radiology (IR) clinic. A thorough description of the research study will be provided. Informed consent will also take place at this time (see below). Once the bloodwork and imaging are reviewed, the patient will be scheduled for the procedure following this clinic visit if they meet criteria and the patient is willing to proceed.

Visit 1 - Screening:

The screening period may take up to 8 weeks to complete. Some of the tests and assessments will be performed at the time of the consultation in Interventional Radiology (IR). Other tests and assessments

will be scheduled at appropriate facilities within the 8-week period. The following will be performed for screening:

- 1) Obtain informed consent
- 2) Collect demographics including age, sex, and race
- 3) Medical history and co-morbidities
- 4) Physical exam to include height, weight, BMI and vital signs
- 5) Evaluation for moderate sedation
- 6) Knee MRI with or without contrast. If performed within 12 months will not need to be repeated. Knee injury and Osteoarthritis Outcome Score (KOOS) questionnaire
- 7) Frequency/dosage of analgesic questionnaire
- 8) 100 mm visual analog pain scale
- 9) Knee x-ray. If performed within 12 months will not need to be repeated.
- 10) 30 second chair stand test
- 11) Pre-procedure labs If performed within 1 month will not need to be repeated:
 - CBC with Platelets
 - o GFR
 - o INR
 - o PTT

Pregnancy test for women of child-bearing potential

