- 5. There are no signs of active bleeding or hemorrhage
- 6. Patient has a safe ride home

After GAE, follow-up will occur at 1 week (\pm 4 days), 1 month (\pm 2 weeks), 3 months (\pm 2 weeks), 6 months (\pm 2 weeks) from the date of treatment.

Visit 3 - 1 week (± 4 days) Post Procedure Phone Call

One week after the GAE procedure, a phone follow-up call will be made to check the on status of the subject. Standard post surgical questions pertaining to infection and pain will be asked. If there are any concerns, an in-person evaluation will be scheduled.

Visit 4 - 1 month (± 2 weeks) Post Procedure

Subjects will have the following assessments performed:

- Physical examination including vital signs
- KOOS and VAS questionnaires
- 30 second chair stand test
- Review of adverse events

Visit 5 - 3 months (± 2 weeks) Post Procedure

Subjects will have the following assessments performed:

- Physical examination including vital signs
- KOOS and VAS questionnaires
- 30 second chair stand test
- Review of adverse events

Visit 6 - 6 months (± 2 weeks) Post Procedure

Subjects will have the following assessments performed:

- Physical examination including vital signs
- KOOS and VAS questionnaires
- 30 second chair stand test
- Review of adverse events

Whenever possible, follow-up phone calls\tele-medicine visits will be made to subjects at 12 and 24months post procedure to obtain updated information on pain.

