2.4.2.1 Study Compliance

Subjects will be required to avoid escalation of conservative therapy during the study period. A review of current and prior conservative treatment measures will be reviewed with each subject during follow-up visits. Any patient that significantly elevates conservative therapy (e.g. initiation of a new medication or therapy not previously used) will be withdrawn from the study.

Early Withdrawal of Subjects:

Subjects will be withdrawn from the study under the following conditions:

- 1 At any point at the patient's discretion
- 2 Any major complication that occurs that prevents the ability to perform/complete the GAE procedure
- 3 Patient is unable to complete at least one follow-up visit

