2.5 Statistical Methods and Data Analysis

2.5.1 Study Endpoints

2.5.1.1 Primary Endpoints

The primary endpoint of this study will be overall efficacy of treatment as determined by an improvement in pain of at least 10 points based on the KOOS Pain questionnaire at 6 months. The null and alternative hypotheses respectively will be: H_0 : Mean_{GAE} = Mean_{Sham} and H_A : Mean_{GAE} \neq Mean_{Sham}, with a two sided test.

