2.5.1.2 Secondary Endpoints

Secondary outcomes will be improvement in functionality and quality of life based on the KOOS Function in Sport and Recreation KOOS, and Quality of Life Scale at 6 months as well as the quantitative functional measures and changes in medication use. To adjust for multiple comparisons, the Holm-Bonferroni correction method will be implemented.

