2.5.2 Sample Size Determination

The Knee Injury and Osteoarthritis Outcome (KOOS) Score which is a primary outcome measure is a measure of patients' knee and associated problems and functionality. It is endorsed by the American Academy of Orthopedic Surgeons, the US Food and Drug Administration, and the International Cartilage Repair Society and has demonstrated reliability for both clinical and research purposes (11). The Visual Analog Scale (VAS) for pain will be used as a secondary outcome measure. This scale is also well-validated and has demonstrated reliability for patients with osteoarthritis (12). The Minimal Clinically Important Difference (MCID) for KOOS has been reported to be ~10. Data on the KOOS indicates a population standard deviation of 15 (koos.nu). Assuming we wish to detect an MCID of 10 points in this population, our targeted effect size is 0.66. A power calculation for a paired t-test (baseline vs 6-month KOOS Pain scores) shows our pilot study of 15 patients would have 22% power.

2.5.3 *Efficacy Analysis*

Comparison of semi-quantitative and quantitative outcome measures will be performed with the appropriate statistics testing. For the pilot group, baseline and endpoint scores will be compared using paired t-tests.

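### Patients who escalate therapy are withdrawn with no rule for counting them at month 6; if they do worse than the rest, mean change and response rate are overstated

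*Combined protocol and SAP*

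**What the plan says.** Section 2.4.2.1 (Study Compliance) bars escalation of conservative therapy during the study and makes withdrawal mandatory: "Any patient that significantly elevates conservative therapy (e.g. initiation of a new medication or therapy not previously used) will be withdrawn from the study". Escalation comes to light through follow-up: "A review of current and prior conservative treatment measures will be reviewed with each subject during follow-up visits". The early-withdrawal list that follows has three other conditions: the patient's choice, a major complication that prevents the procedure, and failure to complete at least one follow-up visit. Escalation is not on that list, and neither text says how a withdrawn patient is analysed.

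The primary endpoint (section 2.5.1.1) is "an improvement in pain of at least 10 points based on the KOOS Pain questionnaire at 6 months"; section B defines clinical success in the same terms. Section 2.5.3 gives the test: "For the pilot group, baseline and endpoint scores will be compared using paired t-tests". Section 2.5.2 identifies the scores: "A power calculation for a paired t-test (baseline vs 6-month KOOS Pain scores) shows our pilot study of 15 patients would have 22% power". Sections 2.5.1 to 2.5.4 contain no analysis set, missing-data method, non-responder rule or sensitivity analysis. Section 2.3.2 expects every patient to complete.

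The secondary outcomes (section 2.5.1.2) include KOOS subscales "as well as the quantitative functional measures and changes in medication use". Screening (Visit 1, section 2.4.1) lists "Frequency/dosage of analgesic questionnaire". Visits 4, 5 and 6 list "KOOS and VAS questionnaires", examination, the chair stand test and adverse events, but not the analgesic questionnaire.

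**The concern.** Patients enter with pain that has not responded to conservative treatment (section 2.3.1). Starting something new is what one would expect of a patient whose pain persists after GAE, though the documents do not establish this. The rule may therefore remove treatment failures selectively, and an analysis of those who remain would flatter the procedure. With 15 patients (section 2.2.1) or 30 (section 2.3.2) and no control arm, a few exclusions can shift the result, and section 2.2.1 gives the series the purpose of demonstrating efficacy as well as safety.

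The medication-use outcome is affected more directly. The protocol's own example of a reason for withdrawal is starting a new medication, so the rule removes patients with an unfavourable result on that outcome. For those who stay, the follow-up data rest on a general treatment review, because the questionnaire is listed only at screening.

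**Working it through.** **Who is lost.** KOOS is taken at months 1, 3 and 6. An escalator withdrawn before visit 6 has no planned 6-month score and cannot enter a paired test of baseline against month 6. Month 1 and 3 scores may exist, but the named test does not use them. Escalation first found at visit 6 may coincide with a score; the plan does not say whether that score counts.

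**The plan's own figure.** Section 2.5.2 gives 22% power. A paired t-test with n = 15, effect size 0.66 and two-sided 5% has 66.2% power; a two-sample test with 15 patients in total (7 + 8) gives 21.9%. That mismatch is a separate matter and nothing below uses it. The 22% power quoted below for a true mean of 5 is a coincidence.

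**Inputs.** Response threshold 10 points (section 2.5.1.1); n = 15 or 30; SD 15 (section 2.5.2, given there as a population SD, used here as an assumed SD of change). Also assumed: normally distributed change; true mean 5 for response and mean change; true mean 0 for false positives; two-sided 5% (stated only for safety, section 2.5.4); no 6-month score for withdrawn patients. Withdrawal rates are assumptions.

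**General identity.** Overstatement of the mean = w × (mean of those kept − mean of those withdrawn), where w is the share withdrawn. If those kept improve by 10 and those withdrawn by 0, w = 20% gives 0.2 × 10 = 2 points.

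**Response formulas.** True response p = 1 − Φ((10 − 5)/15) = 0.369.
- All withdrawn are non-responders: p/(1 − w). At w = 1/15: 0.369/0.933 = 0.396. At w = 0.20: 0.369/0.80 = 0.46.
- Non-responders withdrawn at twice the responders' rate r: r = w/(p + 2(1 − p)), and observed response = p(1 − r)/(1 − w). At w = 0.10: r = 0.10/1.631 = 0.061, so 0.369 × 0.939/0.90 = 0.385.

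**Scenarios, SD 15.** False positives are tests significant in favour of GAE when the true mean is 0 (reference 2.5%), from 100,000 simulated trials per cell.

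| Withdrawn before month 6 | Response (true 37%) | Mean change (true 5) | False positives, n = 15 / 30 |
|---|---|---|---|
| 20%, unrelated to outcome | 37% | 5.0 | 2.5% / 2.5% |
| 5%, two-to-one | 37.7% | 5.2 | 2.8% / 2.9% |
| 10%, two-to-one | 38.5% | 5.4 | 2.9% / 3.2% |
| 20%, two-to-one | 40.5% | 5.9 | 3.5% / 4.1% |
| 1 of 15 or 2 of 30, all non-responders | 39.6% | 5.6–5.7 | 3.3% / 3.6% |
| 20%, all non-responders (extreme) | 46% | 7.2 | 5.9% / 7.7% |

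In the first row the only cost is power at mean 5: 22% falls to 18% (n = 15), and 42% to 35% (n = 30).

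**Other values.**
- SD 10 (true response 31%): the 10% two-to-one case gives 32.3% and false positives of 2.7% / 3.0%; the extreme case gives 38.6% and 4.2% / 5.3%.
- SD 20 (true response 40%): 41.8% and 3.0% / 3.3%; extreme case 50.2% and 7.1% / 9.7%.
- True mean 10, SD 15: the 10% two-to-one case moves response from 50% to 51.9% and the mean from 10 to 10.4.

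**The case against.** The strongest reply is that the effect is small and the exposed group narrow. Only significant escalation triggers withdrawal. No contact is scheduled between months 3 and 6, so escalation starting then would usually surface at visit 6, when KOOS is also taken. The assumed rates must therefore be read as escalation found before visit 6. In the moderate cases (5–10%, two-to-one) the mean moves by 0.2 to 0.4 points, against a standard error of 15/√15 = 3.9 or 15/√30 = 2.7; response moves by 1 to 2 percentage points, when one patient is 6.7 or 3.3. All of this stands. It limits the size of the bias but does not supply the missing rule, and the plan is also silent on scores from escalators found at visit 6.

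Second, leaving escalators out avoids crediting GAE with the added therapy. That is a legitimate reason, but the plan does not give it, and the choice needs to be stated and its effect shown.

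Third, the early-withdrawal item on completing at least one follow-up visit might suggest that one visit keeps a patient in the study. It neither overrides the mandatory withdrawal nor settles month 6.

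Fourth, the missing analgesic questionnaire is a gap even without withdrawals. That is true, but the two gaps affect the same outcome and can be closed together.

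**Conclusion.** The concern holds. The omission is certain from the text; the bias is conditional. It arises only if escalators found before visit 6 do worse than the others. It vanishes if escalation is unrelated to outcome and reverses if they do better. Under the SD 15 assumptions it runs from negligible (37.7% against 37%) to material (46% against 37%, with false positives of 5.9% or 7.7% against 2.5%), and the upper end requires an extreme pattern. No number can be put on the medication-use outcome, but the direction follows from the rule itself if patients who start a new medication are left out. Month 1 and 3 scores could only partly show which case applies. This should be fixed before the 6-month data are examined, so that results cannot influence the choice of rule.

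**What to change.** - Leave the therapy restriction to the investigators, but separate it from data collection. Record each escalation and its date, and continue the scheduled KOOS, VAS and adverse event assessments to month 6 in patients who agree.
- Define the primary set as all patients in whom GAE was attempted, and reconcile this with the early-withdrawal item on complications that prevent the procedure.
- For the 10-point response, count escalation or a missing 6-month score as not achieved, and report the observed rate alongside.
- For mean change, keep the paired t-test on all available 6-month scores, including those after escalation, and say that this credits GAE with the added therapy. Add a sensitivity analysis without those scores. State that the response and mean summaries treat escalation differently and so answer different questions.
- Report how many patients lack a 6-month score, why, and their month 1 and 3 KOOS.
- Add the analgesic questionnaire to visits 4 to 6 and keep escalators in the medication-use analysis.

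The cost is protocol, SAP and consent wording, plus one existing questionnaire at three scheduled visits: at most 15 × 3 = 45 or 30 × 3 = 90 administrations, with no added visits. The response rate may look less favourable. If escalation is unrelated to outcome, counting escalators as failures gives 0.369 × 0.9 = 33% (10% escalate) or 0.369 × 0.8 = 30% (20% escalate) instead of 37%, which is why the observed rate belongs beside it.

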1.0 Purpose of the Investigation

Osteoarthritis is an increasingly prevalent disease and often results in functionally limiting joint pain. In 2015, an estimated 54 million adults (22.7%) in the United States had doctor-diagnosed arthritis, with 43.5% of those patients reporting lifestyle and activity limitations (1).

The knee is a commonly affected joint and results in an annual healthcare expenditure of \$27 billion (2). Definitive therapy for knee osteoarthritis is total knee arthroplasty. An estimated 54% of patients with knee osteoarthritis require a total knee arthroplasty within their lifetime, and 658,000 people undergo surgery annually (2-3). The goal of conservative management is to delay or eliminate the need for a total knee arthroplasty in patients. Currently, patients manage their pain with conservative management for an average of 13 years (2).

First line conservative management is treatment with physical therapy, weight loss, non-steroidal antiinflammatory medications, and corticosteroid injections. Opiate medications are being prescribed with increasing frequency, despite evidence that they do not effectively treat osteoarthritis pain (4).

Early trials have shown transcatheter embolization of abnormal neovasculature with microparticles can be effective in the treatment of mild to moderate knee osteoarthritis refractory to conservative management in select cases (5). This therapy aims to treat the angiogenesis and inflammatory component involved in the pathophysiology of osteoarthritis (6-7).

Thickening and hypertrophy of the knee synovium has a similar appearance on angiography to hypervascular tumors. Transcatheter arterial embolization with permanent and resorbable particles has been shown to be safe in early trials for treatment of knee osteoarthritis as well as in patients being treated for hemarthrosis, with small trials showing no major complications and 8-20% having minor self-resolving skin or puncture site complications (5, 8-9). Additionally, complications do not increase with repeat embolizations (9). The use of resorbable particles has a theoretical advantage as the particles will not permanently reside within tissue.

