2.3.1 General characteristics of the proposed subject population

Similar to prior studies conducted on GAE, subjects included in the study will be those with mild to moderate knee osteoarthritis with moderate to severe pain that is refractory to conservative management. These are patients who have significant symptoms but are not ideal candidates for total knee replacement.

2.3.2 *Anticipated number of research subjects*

For the Pilot Study, 30 patients are expected to enroll (defined as completion of the informed consent process as per University IRB policies) and all are expected to complete the study.

2.3.3 Inclusion Criteria:

1. Patients between ages 18 and 75 with moderate/severe knee pain secondary to primary osteoarthritis. Moderate/severe pain will be defined as pain 30 mm to

100 mm on the Visual Analog Pain Scale (where 0 denotes 'no pain' and 100 mm denotes worst pain imaginable')

- 2. Grade 1, 2, or 3 osteoarthritis on the Kellgren-Lawrence grading scale on knee x-ray in the last 12 months
- 3. Pain must be refractory to 3 months of medical management (which may include a combination of oral analgesics, intraarticular steroids, viscosupplementation, opioid therapy, etc)
- 4. Patients willing and able to consent to the study

2.3.4 Exclusion Criteria:

- 1 Kidney dysfunction defined as an estimated GFR < 60 mL/min
- 2 Acute knee injury
- 3 Current local infection
- 4 Prior ipsilateral knee replacement surgery
- 5 Infectious or inflammatory arthritis
- 6 History of contrast allergy resulting in anaphylaxis
- 7 INR (International Normalization Ratio) > 1.6
- 8 Platelets < 50,000
- 9 Significant atherosclerosis that would limit angiography
- 10 Active malignancy
- 11 Active pregnancy
- 12 Appropriate candidate for knee replacement surgery determined by clinical and physical examination
- 13 Recent within 3 months, or active cigarette user
- 14 Any other condition that in the opinion of the investigator would preclude the patient from participation.

2.4 Study Procedures:

2.4.1 Patient Recruitment:

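### The plan has no rule for a 6-month KOOS Pain score taken after surgery or a further injection to the treated knee, so by default it is analysed as a GAE result

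*Combined protocol and SAP*

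**What the plan says.** Section 2.4.2.1 opens with a general restriction: "Subjects will be required to avoid escalation of conservative therapy during the study period". It then plans monitoring: "A review of current and prior conservative treatment measures will be reviewed with each subject during follow-up visits". The consequence is that any patient who "significantly elevates conservative therapy (e.g. initiation of a new medication or therapy not previously used") is withdrawn. The degree of increase that triggers withdrawal is not defined. The early-withdrawal list that follows names patient choice, a major complication that prevents the procedure, and failure to complete any follow-up visit.

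Inclusion criterion 3 (section 2.3.3) admits patients whose earlier management is one "which may include a combination of oral analgesics, intraarticular steroids, viscosupplementation, opioid therapy, etc". Section 1.0 places steroid injection within conservative care: "First line conservative management is treatment with physical therapy, weight loss, non-steroidal antiinflammatory medications, and corticosteroid injections". It places replacement outside it: "Definitive therapy for knee osteoarthritis is total knee arthroplasty". Section 3.1 names knee replacement as the usual next option for this population. In section 2.3.4 replacement appears only at entry, as exclusions 4 and 12.

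The primary endpoint (2.5.1.1) is an improvement of at least 10 points in KOOS Pain at 6 months. Section 2.5.3 compares baseline and endpoint scores by paired t-test. Neither section mentions scores obtained after another treatment to the knee, or the data of withdrawn patients. After month 6, calls are made where possible to "subjects at 12 and 24months post procedure to obtain updated information on pain".

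**The concern.** The trial is meant to show what GAE does to knee pain. A patient for whom GAE fails may receive another treatment to the same knee before month 6, and the 6-month score then reflects both. If that score is used as it stands, a treatment failure can appear as a success. The hypotheses in 2.5.1.1 refer to a sham mean, but the pilot has one treated group and a before/after comparison, so no control arm would reveal the effect.

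Recording is also thin. The assessment lists for Visits 4 to 6 contain no item for interventions to the knee, the analgesic questionnaire is listed only at screening, and the later calls are described as asking about pain. The treatment review in 2.4.2.1 is confined to conservative measures. Adverse-effect reporting need not flag a replacement either: under 3.2.1, admission for a pre-existing condition that has not worsened is not in itself a serious adverse effect.

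**Working it through.** **What the text reaches**

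| Event in the treated knee after GAE | Escalation rule, 2.4.2.1 | Early-withdrawal list | Score rule, 2.5.1.1 and 2.5.3 |
|---|---|---|---|
| New drug or therapy | Yes, by the example | Not named | None |
| Repeat or more frequent injection | Judgement: barred if it is an escalation, withdrawn if significant | Not named | None |
| Repeat embolization | Not conservative therapy | Not named | None |
| Knee replacement or other surgery | Not conservative therapy | Not named | None |

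KOOS, VAS and the treatment review all belong to the same follow-up visits. The judgement on an injection can therefore be made by someone who already knows the scores.

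**Size**

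The plan gives no figure on this point. Its one computed design figure, 22% power for 15 patients, plays no part here. (It does not reproduce as the paired t-test named beside it: effect size 0.66, n = 15 and an assumed two-sided 5% level give 66.2%.)

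Inputs from the documents: n = 15 (2.2.1, 2.5.2) or 30 (2.3.2); target 10 points and SD 15 (2.5.2). Assumptions: the number of patients k who have another treatment and stay in the analysis, and the gain X it gives each of them.

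Shift in mean change = kX/n.
- One patient gaining 40: 40/15 = 2.7 points; with 30 patients, 40/30 = 1.3.
- Three patients gaining 10: 3 × 10/15 = 2.0.
- One patient gaining 10: 10/15 = 0.7.

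One patient wrongly counted as a responder adds 1/15 = 6.7 percentage points to the response rate, or 1/30 = 3.3. This holds only if that patient would not otherwise have responded.

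A simulation (40,000 trials per row) assumed a true GAE change of 0 and an SD of change of 15. The documents give 15 as a population SD; it equals the SD of change if the two time points correlate at 0.5, since 15 × √(2 × 0.5) = 15. With no other treatment, a falsely significant improvement has probability 2.5% and the expected 10-point response rate is 1 − Φ(10/15) = 25.2%.

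| n | k | X | Mean shift | False significant improvement | 10-point response |
|---|---|---|---|---|---|
| 15 | 1 | 10 | 0.7 | 3.3% | 26.8% |
| 15 | 1 | 40 | 2.7 | 4.4% | 30.1% |
| 15 | 3 | 10 | 2.0 | 6.2% | 30.3% |
| 15 | 2 | 20 | 2.7 | 6.8% | 32.0% |
| 15 | 3 | 40 | 8.0 | 16.5% | 39.7% |
| 30 | 4 | 20 | 2.7 | 11.2% | 31.9% |
| 30 | 6 | 40 | 8.0 | 47.1% | 39.8% |

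**Why dropping the score is not the remedy**

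Suppose 14 patients improve by 10 points on average, and one gains nothing from GAE but 40 from surgery.
- Score kept: (14 × 10 + 40)/15 = 12.0.
- Patient dropped: 140/14 = 10.0.
- Change set to zero: 140/15 = 9.3.

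Under these assumptions 9.3 is the mean GAE effect. Dropping the patient still overstates it.

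**The case against.** A reader might infer that the rule depends on whether a therapy was used before, so that repeat injections are exempt. The documents do not support this. The new-therapy wording is only an example, and the preceding sentence bars escalation in general. Steroid injection is classed as conservative care. The instructions for the month before GAE (2.4.1, Visit 2) separate starting a therapy from escalating one already in use, so escalation includes the latter. A repeat injection can therefore be caught; what is missing is a threshold.

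A reader might also infer that the plan directs these scores to be kept as benefit. No section says so. It is what the stated analysis does by default when nothing else is specified.

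The replacement risk should not be overstated. Exclusion 12 removes appropriate replacement candidates at entry, and section 1.0 gives an average of 13 years of conservative management. The 54% lifetime figure there gives no rate for 6 months. The later calls have no stated efficacy analysis, so a claim that the two-year result is biased has little to attach to yet.

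For injections at an unchanged frequency the direction of bias is unclear. Baseline may carry an injection effect too, so the net bias could be zero or negative. That objection stands, and is why such use belongs in a sensitivity analysis. It does not answer the absence of any rule for surgery or for scores after another knee treatment.

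**Conclusion.** The concern holds in this form: surgery to the treated knee after GAE falls outside 2.4.2.1, repeat injections rest on an undefined threshold, and the analysis has no rule for the score that follows either. With surgery, or with a new or increased injection that goes unrecognised, the default favours GAE.

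The size cannot be fixed from the documents, because event counts and gains are assumed. It is small for one modest case (0.7 points; false significance 3.3% against 2.5%) and material if a fifth of patients gain a lot (8.0 points against the 10-point target; 16.5% with 15 patients). It should be corrected before analysis: the remedy is cheap, and a judgement made once the scores are known cannot be repaired afterwards.

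**What to change.** These changes concern recording and analysis only.

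1. At Visits 4 to 6 and in the 12- and 24-month calls, record and date any intra-articular injection, repeat embolization or surgery to the treated knee. For injections, record the pre-entry frequency so that an increase can be recognised.
2. In 2.5.3, count a patient with knee replacement or other surgery to the treated knee, repeat embolization, or new or increased injection before month 6 as not reaching the 10-point endpoint. Keep the patient in the denominator, including when 2.4.2.1 leads to withdrawal.
3. In the paired t-test, replace the post-event score with a prespecified unfavourable value, for example a change of zero, and do not drop the patient. Report the observed scores separately.
4. Add two sensitivity analyses: one that also counts injections at unchanged pre-entry frequency as failure, and one that uses all observed scores.
5. Apply the same flag to any pain result reported at 12 or 24 months.

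The cost is a short dated checklist added to the treatment review already planned, and a few sentences in 2.4.2.1 and 2.5.3. The reported response rate and mean change may be slightly lower.
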